4.2 Scientific Rationale for Study Design

This study evaluates the safety, tolerability, and PK of ascending multiple doses of TCK-276 administered as oral tablet(s). The design is standard and is considered appropriate to meet the objectives of this exploratory study.

A double-blind, placebo-controlled study is appropriate and standard for an ascending multiple dose study. This design will minimize bias and provide reference data (i.e., data from placebo-treated patients) which will aid in the interpretation of results. The SRC will review available blinded safety, tolerability, and PK data after each cohort to confirm whether it is safe to proceed with the next planned dose, whether the dose escalation should be stopped, or if the dose should be lowered, repeated or titrated in the subsequent cohort.

The safety assessments for the study are accepted measures for ensuring safety of patients during a clinical study. The PK sampling schedule is considered appropriate given the information available. The justification for dose selection is discussed in Section 4.3.

4.3 Justification for Dose

In the SAD study, which included dose-levels up to 185 mg (capsule), TCK-276 was generally safe and well tolerated in healthy subjects with no reports of SAEs nor discontinuations due to AEs. The starting dose for the MAD study (10 mg, tablet) is sufficiently lower than the highest dose in the SAD study (185 mg, capsule), and the projected clinical effective dose (75 mg) that was calculated from nonclinical pharmacological study using the rat adjuvant-induced arthritis model.

Patients with RA will be enrolled in this MAD study. Given the data for recently approved RA drugs, an up to 2-fold increased exposure in patients with RA compared to healthy subjects was taken into consideration as a conservative approach. Even if a 2-fold higher exposure in patients with RA would occur, the exposure of the 10 mg in the MAD study corresponds to 20 mg in healthy subjects, which is sufficiently lower than that of the highest dose in the SAD study (185 mg) and the projected clinical effective dose (75 mg).

Therefore, 10 mg as tablet formulation is considered the appropriate starting dose in the MAD study.

The dosing frequency (i.e., QD) was selected considering the PK characteristics of TCK-276 and patient's convenience. The dosing duration (7 days) was considered sufficient to achieve steady state conditions.

Dose Escalation

In this MAD study, the dose escalation progression will be from 10, 25, 75, and up to 150 mg in subsequent cohorts. The overall exposure to TCK-276 (in terms of geometric mean AUC_{tau}) on Day 7 is not expected to exceed the predefined AUC cap [REDACTED]. The exposure at 150 mg dosing in tablet formulation is assumed to be less than the predefined AUC cap based on the results from the SAD study (5 mg to 185 mg, capsule). Therefore, 150 mg is chosen for the highest dose. The dose in Cohorts 2, 3, and 4 may be adjusted based on the safety and PK results from the previous cohorts, if necessary. Dose escalation will only be allowed after blinded assessment of all safety, tolerability, and available PK data up to Day 10 from each previous cohort evaluated by Investigators, Medical Monitor, and Sponsor representatives during the SRC meeting.

4.4 End of Study Definition

The end of the study is defined as the date of the last visit of the last patient in the study or last scheduled procedure shown in the Schedule of Activities (SoA) ([Table 1-1](#)).

A patient is considered to have completed the study if he/she has completed all periods of the study including the last visit.

5 Study Population

Prospective approval of protocol deviations to recruitment and enrollment criteria, also known as protocol waivers or exemptions, is not permitted.

The study population will consist of patients with RA. Patients must be able to provide written consent and meet all the inclusion criteria and none of the exclusion criteria.

5.1 Inclusion Criteria

Patients who meet the following criteria will be considered eligible to participate in the clinical study:

1. Patient voluntarily agrees to participate in this study and signs an Institutional Review Board (IRB) approved informed consent prior to performing any of the Screening Visit procedures.
2. Patient is able to understand and is willing to comply with all study requirements, and willing to follow the instructions of the study staff.

3. Diagnosis of RA and meeting the 2010 American College of Rheumatology/European League Against Rheumatism classification criteria for RA⁹ (total score 6 or greater/10 diagnosed at least 3 months prior to the Screening Visit).
4. Patient between the ages of 18 and 64 years, inclusive, at the Screening Visit.
5. Female patient must be not pregnant, not breast feeding and one of the following conditions need to apply:
 - a. Of non-childbearing potential based on documented surgical treatment (hysterectomy, bilateral salpingectomy, bilateral oophorectomy) or post-menopausal, meaning patient had spontaneous amenorrhea for at least 12 months without alternate medical cause prior to Screening Visit and follicle stimulating hormone (FSH) > 40 U/mL at the Screening Visit.

OR

- b. Of childbearing potential and using a highly effective method of contraception (failure rate of < 1% per year) and agrees to remain on a highly effective method from the time of signing the informed consent form (ICF) until 21 days after the last dose.
6. Male patient must agree to stay abstinent or must use together with his female partner(s) a form of highly effective contraceptive (failure rate of < 1% per year) from the time of signing the ICF until up to 3 months after the last dose of the study drug.
7. Nonsmokers (or other nicotine use) as determined by history (no nicotine use over the past one year prior to the Screening Visit) and by negative urine cotinine concentration (< 200 ng/mL) at the Screening Visit and at Admission.
8. Body mass index (BMI) between 18.5 and 32.0 kg/m², inclusive, at the Screening Visit.
9. Patient is required to have completed a COVID-19 vaccine regimen within no more than 5 months prior to screening to be eligible for the study.
10. Permitted concomitant medications for any reason, must be on a stable dose (12 weeks for methotrexate and anti-malarials and at least 30 days for other medications prior to the Screening Visit).

Permitted medications include: anti-malarials; nonsteroidal anti-inflammatory drugs including selective cyclooxygenase-2 inhibitors at approved dosage, and low dose oral corticosteroids (prednisone ≤ 10 mg/day or equivalent); methotrexate ≤ 25 mg by mouth (PO) or subcutaneous (SC) weekly concomitantly with folic acid or folinic acid.

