10.4 Appendix 4: Contraceptive and Barrier Guidance

10.4.1 Definitions

Women of Childbearing Potential (WOCBP)

A woman is considered fertile following menarche and until becoming post-menopausal unless permanently sterile (see below).

Women in the following categories are not considered to be a woman of childbearing potential:

1. Premenarchal
2. Premenopausal female with one of the following:
 - Documented hysterectomy
 - Documented bilateral salpingectomy
 - Documented tubal ligation
 - Documented bilateral oophorectomy
3. Post-menopausal female
 - A post-menopausal state is defined as no menses for 12 months without an alternative medical cause. A high FSH level in the post-menopausal range (> 40 U/mL) may be used to confirm a post-menopausal state in women not using hormonal contraception or hormonal replacement therapy (HRT). However, in the absence of 12 months of amenorrhea, a single FSH measurement is insufficient.

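### The FSH cut-off in criterion 5a and Appendix 4 is printed in U/mL, which closes the non-surgical post-menopausal route if mIU/mL was meant, and the two sections disagree on whether FSH is required

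*Protocol*

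**What the plan says.** Criterion 5 of Protocol Section 5.1 gives female patients two ways in.

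- **5a, non-childbearing potential.** This covers "documented surgical treatment (hysterectomy, bilateral salpingectomy, bilateral oophorectomy) or post-menopausal". The post-menopausal branch needs at least 12 months of spontaneous amenorrhea and also "follicle stimulating hormone (FSH) > 40 U/mL at the Screening Visit". The surgical branch carries no FSH condition.
- **5b, childbearing potential.** The wording is "Of childbearing potential and using a highly effective method of contraception", to be kept up until 21 days after the last dose.

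Appendix 4 (Section 10.4.1) defines the same state without FSH: "A post-menopausal state is defined as no menses for 12 months without an alternative medical cause". It then adds "A high FSH level in the post-menopausal range (> 40 U/mL) may be used to confirm a post-menopausal state", and restricts this use to women taking neither hormonal contraception nor hormone replacement.

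The Schedule of Activities (Table 1-1), Section 8.2.5 and Table 10-1 all call for FSH at Screening in post-menopausal women. None of them gives a unit or a reference range, and neither does the laboratory list in SAP Section 6.3. Sections 5 and 8 of the protocol both rule out waivers.

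**The concern.** Two separate matters arise.

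The first is the unit. A threshold in U/mL is 1,000 times the same number in mU/mL. If FSH is reported in mIU/mL, the printed value lies far outside anything a patient could show. It is an operative eligibility threshold: screening tests are run by each local laboratory in a multi-center study, and 5a is where a site looks for the number. A site that follows the text would turn away women on this branch. A site that silently substitutes another unit would be applying a criterion that was not approved, and each such enrollment could be recorded as an inclusion deviation.

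The second is the role of the test. Whatever the unit, 5a and Appendix 4 can classify the same woman differently. The classification decides who must use highly effective contraception, for a drug that Section 2.2.1 reports as teratogenic in rats and rabbits and for which Section 8.4.6 lists embryo-fetal toxicity as an event of special interest.

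**Working it through.** **Inputs from the documents**
- Threshold: > 40 U/mL (Protocol Sections 5.1 and 10.4.1).
- Link between amenorrhea and FSH in 5a: both required.
- Waivers: not permitted (Sections 5 and 8).

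**Inputs assumed, because the documents do not give them**
- Reporting unit: mIU/mL, equal to IU/L.
- Post-menopausal FSH: about 20 to 200 mIU/mL.

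**Step 1: the plan's own figure.** The cut-off is stated without a derivation, so there is no calculation to reproduce. It is the same in both places.

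**Step 2: conversion.** 1 U = 1,000 mU, so 40 U/mL × 1,000 = 40,000 mU/mL. If 40 mIU/mL was meant, that is 40 / 1,000 = 0.04 U/mL, and the printed value is 40 / 0.04 = 1,000 times higher.

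**Step 3: distance from the assumed range.** Ratio = 40,000 / assumed FSH in mIU/mL.

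| Assumed FSH (mIU/mL) | In U/mL | Printed threshold / assumed value |
|---|---|---|
| 20 | 0.020 | 2,000 |
| 25 | 0.025 | 1,600 |
| 40 | 0.040 | 1,000 |
| 100 | 0.100 | 400 |
| 150 | 0.150 | 267 |
| 200 | 0.200 | 200 |

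No value in the range reaches the threshold. The result does not depend on where in the range a patient falls.

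**Step 4: who is caught.**
- A woman with documented hysterectomy, bilateral salpingectomy or bilateral oophorectomy meets 5a without FSH. She is not affected.
- A woman with 12 months of amenorrhea and no listed surgery needs the FSH value. Under the assumptions in Step 3 she cannot meet 5a.
- Her position under 5b is unclear. If 5a alone settles who is of non-childbearing potential, failing it could leave her in 5b. Under Appendix 4 she is not of childbearing potential, so 5b does not describe her.

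**Step 5: the role of FSH, set side by side.** This needs no assumption about units.

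| Place in the protocol | FSH in post-menopausal women |
|---|---|
| 5.1, criterion 5a | Value is a condition of entry; no exception for hormone users |
| Table 1-1, Section 8.2.5, Table 10-1 | Test called for at Screening; no threshold |
| 10.4.1 (Appendix 4) | Not part of the definition; "may be used to confirm a post-menopausal state in women not using hormonal contraception" or hormone replacement |

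The conflict in Step 5 does not make the threshold unattainable. Only the unit does that.

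**The case against.** The strongest objection is that the unit error cannot be shown from the documents. U/mL is used consistently, no other FSH unit or reference range appears, and the usual reporting unit is outside knowledge. This stands, so the unit point is conditional. Consistency is weak support for the printed unit, however, since the same slip could have been carried from one section to the other. Appendix 4 also describes the cut-off as lying in the post-menopausal range, so an attainable value was intended.

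It can also be said that Section 5 governs eligibility, that an entry criterion may be stricter than a general definition, and that the schedule, Section 8.2.5 and Table 10-1 side with 5a in calling for the test. That is fair, and it leaves Appendix 4 as the outlier. The two definitions still differ in one protocol, and the question of hormone users is left open. How far that question matters in practice cannot be judged fully, because the list of prohibited and cautioned medications is redacted.

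Finally, many sites would recognise a unit slip, so wholesale exclusion is improbable. That lowers the likely harm without making the text correct.

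A reader might infer that no naturally post-menopausal woman can enroll. The documents do not support this: the surgical branch needs no FSH, 5b is unclear and not closed, and the barrier rests on an assumed unit. A reader might also want a count of affected patients among the 32. No sex split or menopausal share is given, so any count would be a guess.

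**Conclusion.** The concern holds in a limited form. Both sections print 40 U/mL, which is 40,000 mU/mL. Under the two stated assumptions on unit and range, the threshold is 200 to 2,000 times too high, and the non-surgical post-menopausal branch of 5a cannot be met as written, with no waiver available. If laboratories in fact report on a scale where 40 U/mL is attainable, this part falls away.

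The disagreement over whether FSH is required, and in whom, stands on the text alone.

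The effect is on eligibility, on classification for contraception and on deviation records. Nothing in the analysis changes: Section 9.4 reports no formal sample size calculation, and no endpoint or summary uses FSH.

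**What to change.** 1. Check the FSH unit against the reporting unit of the laboratories that run the screening tests, and correct it in both Section 5.1 and Section 10.4.1. Correcting only one would leave a new contradiction. Stating the unit beside FSH in Table 10-1 would help sites.
2. Reconcile criterion 5a and Appendix 4 so that they give one definition of post-menopausal status. It should say whether the FSH value is required or confirmatory, how women on hormonal contraception or hormone replacement are handled, and whether a woman with 12 months of amenorrhea who misses the value may enter under 5b. Which rule to adopt is for the sponsor's clinical team.
3. If patients have already been screened, review how sites applied the cut-off, so that deviations are recorded in the same way everywhere.

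The text changes amount to two unit corrections and one reconciled clause, in the next amendment or a clarification letter. The statistical analyses in the SAP need no change.

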2.2 Background

2.2.1 Summary of Findings from Non-clinical Studies with Potential Clinical Relevance

[figure not shown]
Pharmacodynamic (PD) studies demonstrated that TCK-276 inhibits CDK4/6 and has minimal potential for off-target kinase activity (Sections 5.1.1.2 and 5.1.2 of the Investigator's Brochure [IB]⁷).

[figure not shown]
Results of *in vitro* pharmacology study using rheumatoid arthritis synovial fibroblasts (RASF) indicated that TCK-276 inhibited proliferation and MMP-3 production of RASF (Section 5.1.1.2.5 and 5.1.1.2.6 of the IB).

Results of *in vivo* pharmacology studies using rat and mouse arthritis models, indicated that TCK-276 at ≥ 15 mg/kg of tested doses was effective in the treatment of arthritis with no effect on bone marrow nucleated cells in rat arthritis model and TCK-276 at doses of ≥ 6.25 mg/kg was effective in the treatment of arthritis and bone destruction in mouse arthritis model (Sections 5.1.1.3.1 and 5.1.1.3.2 of the IB⁷).

Safety pharmacology studies were performed *in vitro* and *in vivo* (cardiovascular, central nervous, and respiratory systems) in rats and monkeys. No untoward effects were observed in these studies.

TCK-276 was not genotoxic based on the absence of mutagenic potential in bacterial reverse mutation, the absence of potential for inducing chromosomal aberration in human lymphocytes *in vitro* and in rat bone marrow *in vivo* (Section 5.3.3.2 of the IB⁷).

Embryo-fetal development studies have revealed evidence for teratogenicity in rats and rabbits and post-implantation loss (embryotoxicity) in rabbits (Section 5.3.5.3 of the IB⁷). In the male fertility study, there were no effects on the reproductive function of males or on early embryonic development when treated males were mated with untreated females (Section 5.3.5.1 of the IB⁷).

Based on the non-good laboratory practice preliminary phototoxicity study (non-good laboratory practice grade), TCK-276 is considered to have no phototoxic potential (Section 5.3.7.1 of the IB⁷).

In summary, the preclinical program supports the clinical development of TCK-276, as a once daily, self-administered, oral product for RA treatment. Collectively, the available data indicate that TCK-276 can be useful in the treatment of RA.

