8.4.6 Adverse events of Special Interest

An AESI (serious or non-serious) is one of scientific and medical concern specific to the Sponsor's product or program, for which ongoing monitoring and rapid communication by the Investigator to the Sponsor can be appropriate. Such an event might warrant further investigation to characterize and understand it. Depending on the nature of the event, rapid communication by the Sponsor to other parties might also be warranted.

AESIs are required to be reported by the Investigator to the Sponsor immediately (i.e., within 24 hours after learning of the event) regardless of their causality to the study treatment. The most appropriate diagnosis or if a diagnosis cannot be established, the abnormal laboratory values should be recorded on the eCRF and reported to the Sponsor immediately (i.e., within 24 hours after learning of the event), either as a SAE or an AESI. Based on CDK4/6 inhibition mechanism of action, the following AEs will be defined as AESIs:

- Myelosuppression: Hematology including monitoring for neutropenia, leucopenia, thrombocytopenia, and increased tendency to bleed
- Embryo-fetal toxicity: highly effective methods of contraception will be used by the patients until 21 days after receiving the study drug
- Interstitial lung disease: Pulmonary symptoms (dyspnea, pyrexia, and cough)
- Gastrointestinal toxicity: e.g., diarrhea, nausea, vomiting, and abdominal pain

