10.4.2 Contraception Guidance

Male patients

Male patients with female partners of childbearing potential (including partners who are pregnant or breastfeeding [including pumping breast milk to feed to a child]) must use contraception if any of the following criteria are met:

- Genotoxic study medication
- Study medication where reproductive toxicology studies have not yet been conducted

- Study medication with demonstrated or suspected human teratogenicity/fetotoxicity at subtherapeutic exposure levels if relevant systemic concentrations may be achieved in WOCBP from exposure to seminal fluid

Male patients with female partners of childbearing potential are eligible to participate if they agree to ONE of the following during the protocol-defined time frame:

- Are abstinent from penile-vaginal intercourse as their usual and preferred lifestyle (abstinent on a long term and persistent basis) and agree to remain abstinent.
- Agree to use a male condom plus partner use of a contraceptive method with a failure rate of < 1% per year as described in the table below when having penile-vaginal intercourse with a WOCBP who is not currently pregnant.
- Agree to use a male condom when having penile-vaginal intercourse WOCBP who is currently pregnant.

In addition, male patients must refrain from donating sperm for the duration of the study and for 3 months after the final dose of study medication.

Male patients with a pregnant or breastfeeding (including pumping breast milk to feed to a child) partner must agree to remain abstinent from penile vaginal intercourse or use a male condom during each episode of penile penetration during the study and for at least 3 months after the final dose of study medication.

Female patients

Female patients of childbearing potential are eligible to participate if they agree to use a highly effective method of contraception consistently and correctly as described in the table below. If the Investigator has another method not listed below but is proven to have a failure rate < 1%, then this method may be considered after discussion with the Medical Monitor or Sponsor study physician.

Highly Effective Contraceptive Methods

Highly Effective Contraceptive Methods That Are User Dependent

- Failure rate of < 1% per year when used consistently and correctly.
- Combined (estrogen and progestogen containing) hormonal contraception associated with inhibition of ovulation
 - Oral

- Intravaginal
 - Transdermal

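### Inclusion criterion 6 and Appendix 4 state the male contraception requirement differently, so a man can be eligible under one text and ineligible under the other

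*Protocol*

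**What the plan says.** Three places in the protocol bear on contraception for men.

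- **Section 5.1, inclusion criterion 6.** "Male patient must agree to stay abstinent or must use together with his female partner(s) a form of highly effective contraceptive", with a failure rate below 1% per year, from consent "until up to 3 months after the last dose of the study drug". It covers every male patient and does not mention a condom.
- **Section 10.4.2 (Appendix 4), male patients.** It opens with a condition: men with partners of childbearing potential, including pregnant or breastfeeding partners, "must use contraception if any of the following criteria are met". Three toxicology criteria follow. A second paragraph, which carries no such condition, makes these men eligible if they agree to one of three options: abstinence as an established way of life, "Agree to use a male condom plus partner use of a contraceptive method" with a failure rate below 1% per year, or a condom when the partner is currently pregnant. A later paragraph sets a minimum of 3 months after the final dose for men with a pregnant or breastfeeding partner. Sperm donation is barred for 3 months.
- **Section 8.4.6, embryo-fetal toxicity.** "highly effective methods of contraception will be used by the patients until 21 days after receiving the study drug". No sex is named. Criterion 5b in Section 5.1 gives women of childbearing potential the same 21 days after the last dose.

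Three other statements matter here. Section 5 requires patients to meet all inclusion criteria and bars waivers. Section 8.4.5 ties the period for collecting pregnancies, including those in partners of male patients, to the contraception period in Section 5.1. Section 2.2.1 reports that "TCK-276 was not genotoxic", that embryo-fetal studies showed teratogenicity in rats and rabbits, and that a male fertility study found no effect on reproductive function or early embryonic development.

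**The concern.** Criterion 6 and the Appendix 4 list both decide whether a man may enter the trial, and they do not admit the same men. Because waivers are barred, a site cannot settle the difference by its own judgement. Whichever text it follows, it may enrol a man whom the other text excludes.

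What is at stake is consistent protection of partners for a drug that was teratogenic in two species and has embryo-fetal toxicity as an adverse event of special interest. The contraception period in Section 5.1 also sets the pregnancy collection window, and a period worded as *up to* 3 months gives that window no firm end.

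**Working it through.** The plan has no figure to reproduce here. The check sets the two eligibility texts side by side and asks, for each situation, whether each text is met.

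| Man's situation | Criterion 6 | Appendix 4 eligibility list |
|---|---|---|
| Partner of childbearing potential, not pregnant, on a highly effective method; no condom | Met | Not met (condom missing) |
| Same partner and method, with condom | Met | Met |
| Pregnant partner; condom only | Not met if read literally (condoms are not among the highly effective methods in Appendix 4) | Met |
| Abstains for the required period only, not as an established way of life | Met | Abstinence option not met |
| Abstinent as an established way of life and agrees to continue | Met | Met |

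The texts disagree in three of the five rows, and in both directions: in two, criterion 6 is the more permissive, and in one Appendix 4 is.

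**The conditional opening of Appendix 4.** The first criterion is genotoxicity, which Section 2.2.1 reports as absent. The second is that reproductive toxicology studies have not yet been done, but Section 2.2.1 reports embryo-fetal and male fertility studies. The third concerns teratogenicity or fetotoxicity at subtherapeutic exposure, "if relevant systemic concentrations may be achieved in WOCBP from exposure to seminal fluid". The visible text does not settle whether it applies to TCK-276. The eligibility list that follows does not refer back to these criteria, so Appendix 4 is also unclear within itself.

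**Duration.** Criterion 6 words 3 months as a ceiling (*up to*). Appendix 4 words it as a floor (*at least*) for men with pregnant or breastfeeding partners. For its three eligibility options it refers only to a period defined in the protocol, presumably that of criterion 6. The figure is the same, but the direction of the limit is not.

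**The 21-day sentence.** Section 8.4.6 speaks of patients in general, and the trial enrols both sexes. Read literally it covers men and disagrees with 3 months. Because it equals the female period in criterion 5b, the likelier explanation is a female rule written without the sex.

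**The case against.** The strongest reply is that this is loose drafting around a single intention. Criterion 6 is silent on condoms and does not forbid them. For most men, meeting the stricter element of each text would satisfy both. Durations centre on 3 months throughout. Patients are confined from Day -1 to Day 10, which covers all dosing. The male fertility study was negative. All of this is fair and limits the practical risk. It does not remove the contradiction, because nothing tells sites to combine the texts, and a man with a pregnant partner is treated differently whichever way one looks.

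A reader might also infer more than the documents support:

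- **Three rival male rules, about ten weeks apart.** The last dose is on Day 7. Twenty-one days later is 7 + 21 = Day 28, and 3 months later, taken as 90 to 92 days, is Day 97 to Day 99. That gap is not a fair measure of the problem. The 21 days match the female period and appear in a list of adverse events of special interest, and a man who stopped then would breach an explicit eligibility criterion.
- **No contraception required if none of the Appendix 4 criteria is met.** Criterion 6 applies regardless, and Appendix 4's own eligibility list carries no such condition.
- **Every male patient affected.** The Appendix 4 male options address men with partners of childbearing potential, including pregnant or breastfeeding ones.
- **The protocol is silent on the third criterion.** This cannot be confirmed. Only the SARS-CoV-2 row of Table 2-1 is visible, and Section 2.3.2 says that monitoring of events of special interest is described in that part of the protocol.

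**Conclusion.** The inconsistency between criterion 6 and Appendix 4 is real and should be corrected. It concerns the method (condom or no condom), the kind of abstinence accepted, and the wording of the 3-month limit. The unqualified 21-day sentence in Section 8.4.6 is secondary.

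The size is modest. The conflict reaches men with partners of childbearing potential. Their number cannot be given, because the documents plan 32 patients without a split by sex. No endpoint, planned analysis or sample size is affected.

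The conclusion rests on reading criterion 6 and the Appendix 4 list as eligibility conditions that both bind, which is how each is worded. Consent documents were not available, so any effect on consent wording is not established. Which rule is clinically right is not judged here.

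**What to change.** Reconcile Sections 5.1, 8.4.6 and 10.4.2 as follows; the sponsor's physicians choose the content.

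1. State one male rule once, in criterion 6, covering the method, what counts as abstinence, and pregnant or breastfeeding partners. Have Appendix 4 and Section 8.4.6 refer to it.
2. Say whether the three conditional criteria in Appendix 4 apply to TCK-276, or remove them.
3. Use one wording for duration in place of *up to* and *at least*, so that the pregnancy collection window in Section 8.4.5 has a defined end.
4. Name the group that the 21-day sentence in Section 8.4.6 covers.

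The cost is wording in a protocol amendment and, if needed, matching consent text. Sample size and analysis do not change.
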